The importance of the proposed research lies in the objective to reconfigure weight loss treatment so as to achieve the intended outcome more efficiently and in a manner that allows greater reach. New technologies now make it feasible to deliver treatment and support behavior change from a distance, reducing the need for burdensome in-person contact. A recent comparative effectiveness trial by Appel and colleagues (2011) demonstrated that a technology-supported INLI that delivers lessons via the web and coaching via telephone can be as effective for fostering weight loss as a traditional in-person delivery method. In that study, those randomized to receive 33 telephone coaching sessions lost approximately as much weight as those receiving in-person support (-4.6kg vs. -5.1kg). Because costs for trained personnel are the most expensive part of any INLI, more efficient treatment requiring fewer sessions would be highly advantageous. An optimized treatment could have a reduced number of sessions (e.g., 12 calls able to be delivered by paraprofessionals), but acquire increased impact by adding other low-cost active components. Several candidate components exist, but none has a known, quantified impact independent of other bundled treatment elements. For example, text messaging for obesity treatment has been bundled with telephone coaching (Patrick et al., 2009; Shrewsbury et al., 2009). Informing the primary care provider (PCP) about the patient's weight loss progress has been confounded with having the physician provide behavioral weight loss treatment or having allied health professionals deliver treatment in high-cost medical space, neither of which is cost-efficient (Wadden et al., 2011; Institute of Medicine [IOM], 2010). Other components, e.g., meal

replacements, have been tested in such expensive formats (e.g., free food provision) as to preclude real world implementation (Look AHEAD, 2007; Wadden et al., 2011). Another example involves the use of peers to provide social support who are given so much training (e.g., 36 hours) that they can more aptly be described as semiprofessionals (Katula et al., 2011).

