3.5 Randomization Method

Randomization, stratified by gender, will be computer-generated using the method of randomly permuted blocks. Participants will be informed of their treatment assignment by telephone. Candidates who, when queried, indicate unwillingness to participate in any condition will not be randomized.

4 Study Procedures

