
4.6.4 Rules for Participant Termination

Participants may withdraw from the study at any time. Permission will be sought to continue to collect outcome data for use in the analysis.

5 Statistical Considerations and Data Analytic Plan

The effects of the five individual intervention components will be examined by means of a factorial experiment (see Table 3) involving the following factors: 1) Number of telephone coaching Sessions (12 vs. 24); 2) PCP receives reports (no vs. yes); 3) Text messaging (not provided vs. provided); 4) Meal replacements (recommended vs. not recommended); 5) Buddy Training (not provided vs. provided). Although each of these intervention components has been part of a bundled weight loss intervention previously found to be successful, none of those studies was designed to estimate the impact of any individual component.

We initially chose a factorial experimental design with 16 experimental conditions, and have been conducting this experiment. We recently decided that a complete factorial experiment, obtained by adding 16 more experimental conditions to the design for a total of 32, would have statistical properties that better suit our scientific objectives. Table 3 shows all 32 experimental conditions, indicating which ones we have been running to date (not shaded) and which ones we propose to run (shaded).

Please note that we are not introducing any new experimental treatments; the conditions are merely different permutations of the same five individual components.

The statistical analysis plan for the data remains essentially the same as was originally submitted. The only difference is that in the previous design there was some aliasing of effects that does not occur in the new design.

Table 3 Experimental Conditions in Opt-In Design, with New Conditions Shaded				
Coaching Sessions	Report to PCP	Text Messages	Meal Replace	Buddy Training
12	NO	NO	NO	NO
12	NO	NO	NO	YES
12	NO	NO	YES	NO
12	NO	NO	YES	YES
12	NO	YES	NO	NO
12	NO	YES	NO	YES
12	NO	YES	YES	NO
12	NO	YES	YES	YES
12	YES	NO	NO	NO
12	YES	NO	NO	YES
12	YES	NO	YES	NO
12	YES	NO	YES	YES
12	YES	YES	NO	NO
12	YES	YES	NO	YES
12	YES	YES	YES	NO
12	YES	YES	YES	YES
24	NO	NO	NO	NO
24	NO	NO	NO	YES
24	NO	NO	YES	NO
24	NO	YES	NO	NO

24	NO	YES	NO	YES
24	NO	YES	YES	NO
24	NO	YES	YES	YES
24	YES	NO	NO	NO
24	YES	NO	NO	YES
24	YES	NO	YES	NO
24	YES	NO	YES	YES
24	YES	YES	NO	NO
24	YES	YES	NO	YES
24	YES	YES	YES	NO
24	YES	YES	YES	YES

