All of the estimated main effects and interactions will be based on all 32 experimental conditions. For example, the main effect of Number of Coaching Sessions will be estimated by comparing the mean of Experimental Conditions with 12 coaching calls in Table 3 vs. the mean of Experimental Conditions with 24 coaching calls. Similarly, the main effect of PCP report will be estimated by comparing the mean of Experimental Conditions having PCP progress reports sent vs. the mean of Experimental Conditions not having PCP progress reports sent. Note that in each case, all experimental subjects are included in the estimate. That is why factorial experiments can have small sample size/condition and still have excellent power if the overall sample size is sufficiently large.

Primary Aim 1 is to test for differences in weight by intervention components across the timepoints (baseline, 3- & 6-months), under an intent-to-treat basis, using linear mixed models. For each of the five components, we will determine whether there is a difference in change across time using baseline as the reference cell (i.e., 3-months vs baseline and 6-months vs baseline). From one perspective this is a main effect of each component on the pre-post difference. However, statistically these effects will be modeled as component by time interactions, with the 6-month outcome as the primary endpoint. We will also include two way interactions between components (e.g., Component 1 by Component 2 by time interaction). We note that (a) testing 2-way interactions between intervention components is extremely novel, as traditional RCTs are not capable of looking at these effects, and (b) because we will be using effect (-1,1) coding rather

than dummy (0,1) coding, the power for tests of main effects and interactions are identical for effects of identical size. We expect that testing these effects will be valuable, as we may find, e.g., that two intervention components each have independent main effects, but that when combined they offer no incremental effect. Our plan for dealing with such cases is elaborated below.

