5.1 Attrition and Nonresponse

Despite our efforts, some attrition and missing data are likely. The linear mixed model does allow missing data and provides valid results under the assumption of missing at random (MAR). MAR means that the missingness can be related to model covariates as well as observed values of the dependent variable, and is sometimes termed "ignorable" missingness. As Molenberghs et. al. (2007) detail, MAR is a relatively weak and non-restrictive assumption about the missing data. Nonetheless, the possibility of non-ignorable missingness cannot be ruled out and so, as advocated by Molenberghs et. al. (2007), we will conduct sensitivity analyses using non-ignorable pattern-mixture and selection models to investigate the robustness of our conclusions across these different models for missing data. This approach will follow our detailed exposition in Chapter 14 of our text (Ackermann & Marrero, 2007).

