5.2 Sample Size and Power

We base power on our primary endpoint: weight change from baseline to the 6-month timepoint. Our interest is in identifying the intervention components that make a more than minimal contribution to average weight loss, or conversely to identify those components that have minimal or no effect on weight loss. Our operational definition of more than minimal is a component effect size of .25 (mean difference divided by standard deviation). Thus, we have powered the study to detect effects of .25 or greater. Using the standard deviation estimate of 4 kg from Amundson et al (2009), which had a follow-up time similar to ours, this translates to a 1 kg difference in weight loss; we view weight loss of less than 1 kg as a minimal effect. There are five components in our 2^{5-1} fractional factorial design. Based on the minimal detectable effect size of .25, the total sample size will be 560 subjects. Based on our previous MBC and PDA+ studies, we conservatively assume an attrition rate of 10% at the 6-month timepoint, so that there will be approximately 504 subjects at this timepoint. Thus, each of the component main effect estimates will be based on 504 subjects, that is, 252 subjects in each of the two levels of the component. Based on these assumptions, we can detect a main effect or interaction effect size of .25 for each component with 80% power under a two-tailed hypothesis test.

Based on our current enrollment as of January 2017, approximately 45% of consented participants were eligible to be randomized after screening. We estimate that we will need to consent approximately 1250 subjects in order to obtain 560 eligible participants for randomization. Of the 560 eligible participants randomized, all will be asked to find a "Buddy" to participate in the study. We are estimating that approximately 850 "Buddies" will need to be verbally consented. (1250 participants + 850 Buddies = 2100 total to be consented).

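### Randomization is stratified by gender, but the primary mixed model names no gender or gender-by-time term, so component standard errors may be slightly too large and the tests mildly conservative (minor).

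*Combined protocol and SAP*

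**What the plan says.** Section 3.5 names one stratification factor: "Randomization, stratified by gender, will be computer-generated using the method of randomly permuted blocks".

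Section 5 describes the primary analysis as a linear mixed model for weight at baseline, 3 and 6 months. It asks "whether there is a difference in change across time using baseline as the reference cell" and says that "these effects will be modeled as component by time interactions, with the 6-month outcome as the primary endpoint". It adds: "We will also include two way interactions between components". No gender term is named there or in the decision steps that follow. Section 5.1 says, in defining missing at random, that "the missingness can be related to model covariates as well as observed values of the dependent variable", but lists no covariates. In the analysis plan gender otherwise appears only as a subgroup in the exploratory moderation analyses (sections 1.5 and 5).

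Section 5.2 sets power at 80% for a component effect of 0.25 SD with 252 participants per level: "Using the standard deviation estimate of 4 kg", this is a 1 kg difference.

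**The concern.** When a stratification factor predicts the outcome, stratified randomization removes its contribution from the sampling variation of the treatment contrast. The model-based standard error reflects this only if the model contains the factor in the form that matters for the contrast. Here the contrast is a change over time, so the relevant term is gender by time. Without it, any gender difference in weight change is counted as residual noise.

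A gender difference is plausible, though the documents do not establish one. The goal in section 4.4 is proportional (7% of body weight) while the outcome is absolute weight, so heavier participants are asked to lose more kilograms.

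What is at stake is limited. Step 1 in section 5 tentatively selects components by the significance of their main effects, and the design has 80% power with no stated margin. A slightly conservative test makes it a little more likely that an active component is dropped.

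**Working it through.** **Inputs from the documents.** 560 randomized and 10% attrition, so 504 analysed and 252 per level; effect 1 kg; SD 4 kg; two-tailed test (section 5.2). At least half female (section 3.3.2). A 4.6 kg loss with telephone coaching in an earlier trial (section 2.1). 7% goal (section 4.4).

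**Assumptions.** Alpha 0.05 (not stated). Share of women p from 0.5 to 0.8. Gender gap in mean 6-month change g:
- 0.9 kg: 4.6 kg over an assumed 100 kg, times an assumed 20 kg gender difference in weight (0.046 × 20 = 0.92).
- 1.4 kg: the full goal on the same 20 kg (0.07 × 20).
- 2 kg: an upper illustration with no source in the documents.

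**Step 1, the plan's own figure.** SE = 4 × √(2/252) = 0.356 kg. Noncentrality = 1/0.356 = 2.81. Power with 502 df = 80.0%. The stated figure reproduces.

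**Step 2, share of variance due to gender.** Taking 4 kg as the total SD, R² = p(1−p)g²/16, and adjustment multiplies the reported SE by √(1−R²). For g = 1.4 and p = 0.5: R² = 0.25 × 1.96/16 = 0.0306, √0.9694 = 0.985, a fall of 1.5%.

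**Step 3, power and type I error.** Because stratification balances gender, the unadjusted estimate already has the within-gender spread, but it is judged against an SE built from the total variance.

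| Gap | Fall in reported SE | Power, no gender | Power, gender by time added | Type I error, no gender |
|---|---|---|---|---|
| 0 kg | 0% | 80.0% | 80.0% | 5.0% |
| 0.9 kg | 0.4–0.6% | 80.1% | 80.3–80.5% | 4.9% |
| 1.4 kg | 1.0–1.5% | 80.2–80.4% | 80.8–81.2% | 4.7–4.8% |
| 2 kg | 2.0–3.2% | 80.5–80.7% | 81.6–82.5% | 4.3–4.6% |

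Ranges run over 50 to 80% women.

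**Step 4, what really changes.** Trials were simulated with gender-stratified blocks over 32 conditions, 10% random loss, five main effects and ten two-way interactions (4,000 runs per setting). Falls in reported SE were 0.4–0.7%, 1.0–1.6% and 2.1–3.2% at 0.9, 1.4 and 2 kg. The sampling SD of the component estimate fell by only 0.0–0.4%; at 2 kg and 50% women it went from 0.3452 to 0.3441. The gain is therefore mainly a correction of the reported SE.

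**Step 5, which term, and which baseline model.** Mixed models were fitted to simulated data with 504 subjects, three visits, unstructured covariance and 50% women, assuming a 20 kg baseline gender difference and a within-gender baseline SD of 14 kg (300 runs). The mean SE of the 6-month component effect, for no gender / gender only / gender plus gender by time, was:
- Component effects at baseline included: 0.3561 / 0.3561 / 0.3502 at 1.4 kg; 0.3554 / 0.3554 / 0.3437 at 2 kg.
- Constrained baseline, gap due only to starting weight: 0.3395 / 0.3445 / 0.3391 at 1.4 kg; 0.3204 / 0.3294 / 0.3201 at 2 kg.
- Constrained baseline, gap unrelated to starting weight: 0.3540 / 0.3557 / 0.3499 at 1.4 kg; 0.3511 / 0.3549 / 0.3431 at 2 kg.

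A gender main effect alone never helps. Under a constrained baseline with a gap due only to starting weight, both terms together lower the SE by about 0.1%.

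**Step 6, the mid-trial design change.** The complete factorial was "obtained by adding 16 more experimental conditions to the design for a total of 32". A 16-condition Resolution V half-fraction has each component at 8 versus 8 conditions, so components stay balanced by gender. Simulating the change (block size assumed, since none is given) left the results essentially the same.

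**The case against.** The strongest reply is that the plan is silent on gender and does not exclude it. Section 5 is a narrative without a model equation, section 5.1 refers to model covariates, and section 5 says the analysis plan is essentially the one first submitted, which is not available here. This stands: the point is a term not named, and the remedy is to name it.

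A second reply is that the size rests on assumption. This also stands. The 0.9 and 1.4 kg gaps both derive from starting weight, the very case in which a constrained-baseline model already absorbs the difference. Section 5 does not say whether component effects at baseline are in the model, so the gain could be close to zero.

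Two stronger readings are tempting, and the documents support neither.
- A reader might infer that the trial falls short of 80% power. That requires 4 kg to be the within-gender SD; unadjusted power at a 2 kg gap would then be 78.3–78.9%. Section 5.2 uses 4 kg as the denominator of an unadjusted standardized difference, which reads naturally as the total SD. On that reading unadjusted power is at least 80.0% at every gap in the table.
- A reader might infer that up to 3% of real precision is being lost. Stratification has already secured nearly all of it (step 4), and the 3% figure needs a 2 kg gap that nothing in the documents supports.

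**Conclusion.** The point holds as a minor one. The model as described does not carry the trial's only stratification factor. If men and women differ in mean weight change, the reported component-by-time standard errors are slightly too large and the Step 1 tests mildly conservative. The size is about 0.4–1.6% of the reported SE and under 1 point of power at assumed gaps of 0.9–1.4 kg, or 2–3% and 1–2 points at an illustrative 2 kg. These figures assume that 4 kg is the total SD, that 50–80% are women, and that component effects at baseline are in the model or that the gap is not explained by starting weight. Otherwise, or with no gap, the gain is about zero. Bias, inflated type I error and an inadequate sample size are not in question.

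**What to change.** State in section 5 that gender and gender by time (3 and 6 months) are fixed effects in the primary mixed model, and carry them into the pattern-mixture and selection models of section 5.1. The time interaction must be named, because gender alone leaves the component-by-time SE unchanged or slightly raises it. In the same place, say whether component effects at baseline are included.

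The cost is one or two sentences and three parameters (gender, gender by 3 months, gender by 6 months) against about 504 subjects. No new data are needed, since gender is already recorded for stratification. If the gap is zero, the SE penalty in a change-score version of the model is about 0.1% at most (√(488/487) = 1.001). Naming the terms in advance also prevents their inclusion from becoming a choice made after the results are seen.

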4.1 Screening/Recruitment

Recruitment will target the channels that have proved successful in our prior Chicago-area studies. These include posting: a) promotions in publications with low advertising cost (*The Red Eye*, *Craig's List*, *The Chicago Reader*, *Google Ad Words*); b) Chicago Transit Authority bus and subway advertisements; c) flyers at downtown area worksites, clinics, and schools; d) clinical trial recruitment announcement on Northwestern University's website; e) social media (Facebook, Twitter, Reddit, Instagram, Metromix, Pinterest); f) relevant websites related to weight loss, health, nutrition, and physical activity that we will solicit to "post" current approved flyers and ads on their sites; g) health registries (Illinois Women's Health Registry at Northwestern University, NU NUCATS, Clinicalconnection.com); h) relevant local health fairs with information booths/tables where brochures and flyers will be available with staff to answer questions, and i) use of the Enterprise Data Warehouse (EDW), a joint initiative of NMFF, NU, and NMH, to recruit patients directly from Northwestern Memorial Hospital's General Internal Medicine Clinic. Postings will list study eligibility criteria and requirements and will provide the study web link, and will not deviate from IRB-approved ad language. The posting will also include a google voice phone number where participants can reach staff if they have any general questions regarding study participation. Registries will send the study coordinator lists of individuals who have agreed to be contacted and we will contact via sending flyers and ads via mail or email, or by calling. At the project's website, interested candidates may consent to research participation and complete on-line screening questionnaires, developed using RedCap, that assess study entry criteria and request good contact times. Scored questionnaire responses will be e-mailed to the laboratory, following which eligible candidates will be contacted by e-mail to arrange for further screening and a telephone interview.

4.1.1 Recruitment Process

On-line screeners assess for eligibility criteria (demographics, weight), physical activity preparedness, motivational readiness to change, and scheduling availability. (b).Telephone screening. Potentially eligible candidates will be contacted by telephone. Study staff will explain the research, ask the patient's interest in participating in the study, and proceed with a verbal informed consent process. Staff will screen for exclusion criteria, including checking all medications to see if any are listed on the study Exclusionary Medication list. In order to flag participants who live together, a study exclusion criteria, [web screeners will be cross-checked for duplicate addresses and phone numbers](#). Candidates who remain interested and eligible will be scheduled for an in-person Orientation session. Those who provide informed consent will be invited to attend the baseline assessment where we will screen further for entry and exclusion criteria as well as gather baseline data. Anthropometric data will be gathered. We will administer the PRIME-MD to screen out candidates who meet criteria for bulimia, current substance abuse or dependence (besides nicotine dependence), or report active suicidal ideation. Eligible participants will also be required to obtain physicians approval and find a buddy in order to participate in the study. Once participants have been scheduled to attend Randomization, they will complete a pre-Randomization telephone call with their potential Lifestyle Coach in the Opt-IN study. This call will be used to develop rapport, as well as minimize withdrawal once participants have been randomized.

4.1.2 Recruitment tracking

The Project Coordinator will track all participants recruited for the study. Participants will initially complete a web survey using RedCap, used by Northwestern University Biomedical

Informatics Center (NUBIC) of the Northwestern University Clinical and Translational Sciences (NUCATS) program. Data from RedCap will be downloaded, and descriptive statistics will be generated. Information to be collected will include participant name, screening date, date of birth, race, ethnicity, self-reported height, self-reported weight (BMI will be automatically calculated), screening status, and reason for exclusion.

4.1.3 Recruitment of Minorities/ Low SES Participants

The Chicago metropolitan area is racially, ethnically, and socio-economically diverse. Of the entire sample, we plan to recruit 55% non-Hispanic Whites, 22% African Americans, 9% Hispanics, 4% other minority (45% minority). Our experience indicates that targeted recruitment of minorities has not been necessary to attain substantial, representative minority enrollment because the Chicago area population is so diverse. However, in the event that these minority groups are not adequately represented in our sample, we plan to target media outlets that are specific to these various ethnic groups.

